13.7.2 Multicenter Issues

Randomization will be stratified by site. Sites will be considered in the primary effectiveness analysis as described in Section 13.3 above. Poolability will be assessed as described in Section 13.3 above.

13.7.3 Multiplicity Issues

Statistical success will require demonstration of non-inferiority in both the primary safety and effectiveness endpoints for the primary analysis populations. Therefore, no adjustments for multiplicity are required for the primary hypothesis tests. The first secondary hypothesis test will be eligible for evaluation only if the primary endpoints are met. Therefore, no adjustment for multiplicity will be necessary. The secondary hypothesis tests in the last family of hypotheses will be adjusted for multiplicity using the Holm stepwise procedure.

14 Quality Control and Quality Assurance

14.1 Study Monitoring

The Sponsor and its representatives must be allowed to visit all study site locations to assess the data, quality, and study integrity in a manner consistent with applicable health authority regulations and the procedures adopted by the Sponsor or its representative.

Prior to the start of the study, member(s) of the Sponsor (or designees) will review the protocol, CRF, regulatory obligations, and other material or equipment relevant to the conduct of the study with the Investigator/Sub-Investigator and relevant study site personnel via an Investigator Meeting and/or site initiation visits.

Monitoring visits and telephone consultations will occur as necessary, or per the monitoring plan, during the course of the investigation to verify the following:

- The rights and well-being of subjects are protected;
- The conduct of the investigation is in compliance with the currently approved protocol/amendment, 21CFR Parts 50, 54, 56, and 812, ISO 15798 (2013(E)) Ophthalmic Implants – Ophthalmic Viscosurgical Devices, and ISO 14155 (2011(E)) Clinical Investigation of Medical Devices for Human Subjects – Good Clinical Practices, 42 USC 282(j) and IRB/EC requirements;
- The integrity of the data, including adequate study documentation;
- The facilities remain acceptable;
- The Investigator and site personnel remains qualified and able to conduct the study; and
- Test article accountability.

During the course of the study, if the Sponsor determines that an Investigator is non-compliant with the study plan and/or applicable regulatory requirements, the Sponsor will take action to secure compliance. In addition, the Sponsor may terminate the Investigator's participation in the study if appropriate, or if the Investigator remains non-compliant despite the Sponsor's actions.

14.2 Source Documentation

All medical information obtained at each study visit must be recorded in the subject's record (source documentation) in real time as it is collected. Source documentation consists of original subject documents, as well as data and records with information relevant to the subject and his/her participation in the study.

Source documentation worksheets may be provided by the Sponsor or its designee to record pertinent information. The completed worksheets can then be incorporated into the subject's medical chart. If it is preferred to not use the worksheets in the subject's permanent record, then the worksheets should be used as a reference to determine the type of study data to record in the subject's permanent record.

14.3 Case Reports Forms and Data Verification

As used in this protocol, the term Case Report Form (CRF) should be understood to refer to an electronic data record or electronic CRF (eCRF) developed as part of the electronic data capture method utilized in this study.

Subject data required by this protocol are to be recorded on eCRFs. The Investigator and his/her study site personnel will be responsible for completing the eCRFs in a timely manner. The Investigator is required to verify that all of the requested information is accurately recorded on the eCRFs. All information requested on the eCRFs needs to be supplied, including subject identification and initials, date(s), assessment values, etc., and any omission or discrepancy will require explanation. All information on eCRFs must be traceable to source documents.

The study monitor will be responsible for reviewing and verifying the data recorded on the eCRFs, utilizing the original source documentation and will query discrepant findings. The Investigator and study site personnel will be responsible for answering all queries in a timely fashion. The eCRFs will be submitted to the Sponsor for quality assurance review, data entry, and statistical analysis.

Following receipt by the Sponsor, all eCRFs will be reviewed for completeness. Single-entry with verification routines and computerized editing routines will be used to reduce data entry errors and identify unusual data for verification prior to statistical analysis.

Corneal ECD data will be collected at each site and sent to a central reading center for analysis. The reading center will be masked to the OVD a subject has received and will provide the Sponsor or its designee with the results of their analysis.

14.4 Recording of Data and Retention of Documents

Subject data recorded on eCRFs during the study will be documented in a coded fashion. The subject will only be identified by the subject number. Confidentiality of subject records must be maintained to ensure adherence to applicable local privacy regulations.

The Investigator must retain essential documents indefinitely after the completion of the study, unless otherwise notified by the Sponsor. The Investigator agrees to adhere to the document retention procedures when signing the protocol Investigator Statement of Approval.

Essential documents include but are not limited to the following:

- IRB/EC approvals for the study protocol, all amendments, ICF(s), and advertisements;
- IRB/EC annual study review;
- IRB/EC correspondence and reports (e.g., SAE reports, protocol deviations, and safety updates);
- regulatory documents (e.g., financial disclosure and delegation of authority forms);
- all source documents;

- CRFs;
- subject's signed ICF;
- Device Investigator Agreement;
- accountability records for the test article(s);
- correspondence from and to the Sponsor; and
- any other documents relevant to the conduct of the study.

Should an Investigator withdraw from the study (e.g., retirement or relocation), study records will be transferred to a mutually agreed upon designee (e.g., another Investigator or a site IRB/EC). The Investigator will provide notice of such transfer in writing to the Sponsor and/or its representative.

14.5 Audits and Inspections

Audits of clinical research activities in accordance with the Sponsor's internal Standard Operating Procedures to evaluate and assure compliance with the principles of GCP may take place. A regulatory authority may also wish to conduct an inspection (during the study or after its completion). If an inspection is requested by a regulatory authority and/or IRB/EC, the Investigator must inform the Sponsor and its representative immediately that this request has been made.

15 Ethics and Administrative Issues

It is the responsibility of the site's principal investigator to assure that all aspects of the ethics review are conducted in accordance with the Declaration of Helsinki as described in the International Council for Harmonisation (ICH) Guideline E6 for Good Clinical Practice (GCP). The protocol and any information supplied to the subject to obtain informed consent, including written informed consent form(s), subject recruitment procedures (e.g., advertisements), and written information to be provided to subjects (information leaflets), will be reviewed and approved by a qualified Institutional Review Board (IRB) or an Ethics Committee (EC) prior to enrollment of participants in the study. Prior to initiation of the study, the Sponsor or its designee will receive documentation of the IRB/EC approval, which specifically identifies the study/protocol, and a list of the IRB/EC committee members. Protocol amendments will be reviewed and approved by the IRB/EC prior to implementation of any changes made to the study design. Investigators submitted progress reports to the IRB/EC in accordance with the IRB/EC requirements.

15.1 Ethical Conduct of the Study

The study will be conducted in accordance with the protocol and ICH GCP guidelines, applicable regulations and guidelines governing clinical study conduct, and the ethical principles that have their origin in the Declaration of Helsinki.

15.2 Ethics Review

The Investigator should ensure that his/her participation in the study, in addition to the protocol, subject recruitment materials (e.g., written information or materials including web pages, radio advertisements, television spots or written text developed to encourage subject

enrollment) and the ICF to be used in this study are approved by their institution IRB/EC, or if not using their institution's IRB/EC, approved by the reviewing central IRB/EC prior to entering any subjects in the study. Documentation of IRB/EC approval of the study protocol and informed consent must be provided to the Sponsor and its designee prior to initiation of the study. In addition, the Investigator must ensure that the reviewing IRB/EC has provided approval for any protocol amendments prior to implementation. If the amendment necessitates a revision to the ICF, the Investigator should ensure the revised form is also submitted to and approved by the Sponsor or its designee and the IRB/EC prior to implementation.

15.3 Written Informed Consent

Before entry into the study, the Investigator or an authorized member of the investigational staff will explain to potential subjects (or their legally acceptable representatives) the aims, methods, reasonably anticipated benefits, and potential hazards of the study, and any discomfort it may entail. The subject (or legally acceptable representative) will be given sufficient time to read the ICF and the opportunity to ask questions. After this explanation and before entry into the study, consent will be appropriately recorded by means of either the subject's or his legally acceptable representative's dated signature. After having obtained the consent, a copy of the signed and dated ICF will be given to the subject.

If the subject (or legally acceptable representative) is unable to read or write, an impartial witness will be present for the entire informed consent process (which included reading and explaining all written information) and will personally date and sign the ICF after the oral consent of the subject (or legally acceptable representative) is obtained.

The ICF will be signed before the performance of any study-related activity.

15.4 Financial Disclosure

Original Financial Disclosure Form (FDF) completed, signed and dated by the PI and sub-investigators and study personnel listed on the Delegation of Authority Log will be collected by the Sponsor or its designee, as applicable, and file in the Trial Master File. A copy of the FDF will be retained in the Investigator Site Binder.

Appendix A: STUDY FLOW CHART

PROCEDURE/ASSESSMENTS	Preop Visit Day -60 to Day -1	Op Visit Day 0	Postop Visit 1 ^a 6 Hours ± 2 hours Postop	Postop Visit 2 24 Hours ± 4 hours Postop	Postop Visit 3 7 Days ± 2 days Postop	Postop Visit 4 30 Days ± 7 days Postop	Postop Visit 5 90 Days ± 14 days Postop
Informed Consent	X						
Demographic Data	X						
Medical History	X						
Urine Pregnancy Test	X	X ^b			X	X	X
Eligibility Criteria	X	X					
Randomization		X					
Fellow Eye Status	X						
Surgical Procedure ^c		X					
Manifest Subjective Refraction	X						X
Uncorrected Distance VA	X		X	X	X	X	X
Best Corrected Distance VA	X						X
Cataract Classification	X						
Slit Lamp Exam	X		X	X	X	X	X
Intraocular Pressure (Goldmann tonometry)	X		X	X	X	X	X
Fundus Exam (Dilated)	X						X
Ultrasound Pachymetry	X			X			X
ECD via specular microscopy of the central cornea	X						X
Concomitant Medications	X	X	X	X	X	X	X
Adverse Events ^d	X	X	X	X	X	X	X

^a Postoperative Visit 1 must occur on the day of surgery.

^b If last urine pregnancy test was more than 21 days after the preoperative visit, test should be repeated.

^c Required details of the surgical procedure are described in [Appendix C](#).

^d The period of collection of AEs starts from informed consent through study exit

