9.1.2 Randomization Method

Subjects will be randomly assigned to one of the two OVD materials according to the randomization scheme to be provided in a computer-generated randomization code by a biostatistician otherwise not involved with the study.

Interactive Response Technology (IRT) will be utilized for randomization in this study. Randomization will be stratified by site, age group and cataract severity. A method other than stratification may be employed to balance randomization. If so, the method will be specified in the SAP. The randomization codes will be established in blocks such that approximately the same number of subjects will be assigned to the DVisc40 OVD or VISCOAT® OVD treatment groups at each site.

Subjects will be randomized to 1 of 2 treatment groups in a ratio of 1:1 (DVisc40:VISCOAT®). Each screened subject will be assigned a unique 5-digit subject number assigned by the site accessing the IRT system. The subject number assigned by the IRT system will consist of the 2-digit investigational center/site number (pre-assigned by Sponsor or its designee) and the 3-digit chronological screening order number starting with 001 (e.g. 01-001, 01-002). The study device kit will be assigned to subjects based on a randomization code and the kit will be dispensed to the subjects at Day 0 (Operative Visit) by the IRT system. The assigned kit number should be recorded in the subject's source documents and applicable case report form. A study device log will document the inventory and dispensing of study device at each investigational center.

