13.3 Sample Size Determination

13.3.1 Incidence of IOP ≥ 30 mmHg

Due to their comparable rheological properties, DVisc40 and VISCOAT® OVDs are expected to demonstrate similar behavior during surgical procedures.

In published studies using VISCOAT®, VISCOAT® performed without anti-IOP prophylactic treatment where the frequency of IOP spikes ≥ 30 mmHg after surgery ranged from 0.0% to 47.5%.⁶⁻²³ Based on these studies the control OVD incidence of subjects who experience at least one IOP observation ≥ 30 mmHg is estimated to be 0.117 (11.7%). A doubling of the control OVD incidence would be problematic and clinically significant, thus the non-inferiority margin will be defined as equal to the expected rate of 0.117 (11.7%).

When the sample size in each group is 165 subjects, a two-group large-sample normal approximation test of proportions with a one-sided 0.050 significance level will have 95.17% power to reject the null hypothesis that the test is inferior to the control (the difference in proportions, $\pi_t - \pi_c$, is 0.117 or greater) in favor of the alternative hypothesis that the test is non-inferior to the control (the difference in proportions, $\pi_t - \pi_c$, is less than 0.117), assuming that the expected difference in proportions is 0.000 and the proportion in the standard group is 0.117.

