13.5.1 Primary Safety Analysis

IOP will be assessed in the study eye using Goldmann tonometry at each scheduled follow-up visit and may be assessed at unscheduled visits.

Subjects with $IOP \geq 30$ mmHg at any follow-up visit ($IOP \geq 30$ mmHg at any follow-up visit, No $IOP \geq 30$ mmHg at any follow-up visit) will be summarized using categorical summary statistics for the Safety Population by actual treatment received in a table. Missing data will not be imputed for this summary table.

Missing IOP values will be imputed using Markov chain Monte Carlo (MCMC) methods. Twenty imputed datasets will be produced using a seed of 1017144149. The variables used in the imputation model will include IOP at baseline and at each of the scheduled postoperative visits. After missing data at scheduled visits has been imputed, unscheduled visit IOP values will be added to each imputed dataset.

Within each imputed dataset, subjects will be classified as belonging to one of the following groups:

- $IOP \geq 30$ mmHg at any follow-up visit
- No $IOP \geq 30$ mmHg at any follow-up visit

This classification will be based on experiencing at least one IOP measurement of 30 mmHg or more at any follow up visit over the entire course of the study. Subjects experiencing one or more IOP spikes will be counted only once.

The difference between test and control in the proportion of subjects with $IOP \geq 30$ mmHg at any follow-up visit and the asymptotic standard error will be estimated separately for each imputation.

An estimated difference between treatment groups and a two-sided asymptotic Wald 95% confidence interval around the difference will be constructed via combination of the proportion differences and standard errors from the imputations. If all the imputations result in the same estimated difference and confidence interval, then the results of a single imputation may be used.

If the upper confidence limit (equivalent to a one-sided upper 95% confidence limit) is less than 0.117 (11.7%), then the null hypothesis of inferiority will be rejected in favor of the alternative hypothesis of non-inferiority. A p-value will also be provided for this one-sided hypothesis test.

The primary safety analysis will be repeated using the Per Protocol Population as a sensitivity analysis with observed data only (i.e. without imputation).

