13.5.3.1.2 Mean Change from Baseline in IOP

Change from baseline in IOP (mm Hg) will be computed as post-op IOP minus baseline IOP and will be summarized using continuous summary statistics for the Safety Population by scheduled Visit and actual treatment received in a table. A statistical model will be constructed by visit with change from baseline in IOP as the dependent variable, treatment group, investigator, as a fixed factor, baseline IOP as a continuous covariate, and subject as a random factor. For each study visit (6 hours post-op and 24 hours post-op), superiority will be claimed for the test OVD in this endpoint if the null hypothesis is rejected.

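### Adjusting the co-primary IOP spike comparison for baseline IOP would be a small, optional gain in precision; the crude analysis in section 13.5.1 is valid as it stands

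*Combined protocol and SAP*

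**What the plan says.** - **Baseline measurement.** The Appendix A row "Intraocular Pressure (Goldmann tonometry") is marked at the preoperative visit and at all five postoperative visits.
- **Co-primary safety analysis (13.5.1).** Missing IOP values are imputed 20 times from a model containing IOP at baseline and at each scheduled postoperative visit. Each eye is then classed as having a spike (at least one IOP of 30 mmHg or more) or not. The difference in proportions "and the asymptotic standard error will be estimated separately for each imputation", and the results are combined into a Wald interval whose upper limit is compared with 0.117. Baseline IOP plays no part after the imputation step.
- **Mean change in IOP at 6 and 24 hours (13.5.3.1.2).** The secondary model includes "baseline IOP as a continuous covariate".
- **Randomization (9.1.2).** Allocation is 1:1, stratified by site, age group and cataract severity. Baseline IOP is not a stratification factor.
- **Sample size (13.3.1).** For 165 per arm, the section states that "a two-group large-sample normal approximation test of proportions with a one-sided 0.050 significance level will have 95.17% power". The inputs behind that figure are a control spike rate of 0.117 and no true difference between the arms. The trial is therefore sized on the same unadjusted comparison that 13.5.1 carries out.

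**The concern.** The co-primary event is crossing a fixed threshold. Exclusion criterion 8 in section 8.2 caps entry IOP at 24 mmHg, and the event is 30 mmHg. An eye that starts at 24 needs a rise of 6 mmHg to be counted, and one that starts at 14 needs a rise of 16. If baseline IOP predicts peak postoperative IOP, part of the eye-to-eye variation in the spike outcome is explainable from a value already on the database, and the crude comparison leaves it in the standard error. Neither stratification nor the model accounts for baseline IOP in this comparison.

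What is at stake is the width of the interval compared with 0.117, and how far a chance imbalance in baseline IOP moves the estimate in the one trial that is run. The validity of the test is not at stake.

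**Working it through.** **Inputs from the documents.** n = 165 per arm, control rate 0.117, true difference 0, margin 0.117, one-sided alpha 0.05 (13.3.1); 1:1 allocation (9.1.2); entry cap 24 mmHg (8.2).

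**Input not in the documents.** The correlation r between baseline and peak postoperative IOP. It is varied over an assumed range of 0.2 to 0.5, with 0 as a reference.

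**Step 1: reproduce the stated power.**

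SE = √(2 × 0.117 × 0.883 / 165) = √0.0012523 = 0.03539.

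Power = Φ(0.117 / 0.03539 − 1.645) = Φ(3.306 − 1.645) = 95.17%, as stated. The expected number of events is 165 × 0.117 ≈ 19 per arm.

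**Step 2: share of variance explained.** Treat peak IOP as a latent normal variable with correlation r to baseline, and define a spike as its top 11.7%. Then R² = Var(P(spike | baseline)) / (0.117 × 0.883). The adjusted SE is 0.03539 × √(1 − R²), and the gain in equivalent sample size per arm is 165 / (1 − R²) − 165.

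| Assumed r | R² | Adjusted SE | Power | Equivalent extra subjects per arm |
|---|---|---|---|---|
| 0 | 0 | 0.0354 | 95.17% | 0 |
| 0.2 | 0.015 | 0.0351 | 95.4% | about 3 |
| 0.3 | 0.036 | 0.0348 | 95.8% | about 6 |
| 0.4 | 0.067 | 0.0342 | 96.2% | about 12 |
| 0.5 | 0.110 | 0.0334 | 96.9% | about 20 |

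**Step 3: check with the entry cap and the actual estimator.** The simulation used 4,000 trials per scenario, with baseline IOP of assumed mean 16 and SD 3, cut at 24 mmHg. It compared a logistic-standardized difference in proportions with the crude difference.

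| Assumed r | Variance ratio, adjusted / crude | Simulated power, crude → adjusted |
|---|---|---|
| 0 | 1.005 | 95.4% → 95.3% |
| 0.2 | 0.989 | 95.3% → 95.6% |
| 0.3 | 0.978 | 95.0% → 95.5% |
| 0.5 | 0.897 | 95.2% → 96.4% |

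The variance removed is 1.1%, 2.2% and 10.3% at r = 0.2, 0.3 and 0.5. Each figure is a little below its counterpart in step 2.

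**Step 4: size of a chance imbalance.** In the step 2 model the spike rate changes by about φ(1.190) × r = 0.1965 × r per SD of baseline IOP. A two-standard-error imbalance is 2 × √(2/165) = 0.220 SD. At r = 0.3 the shift in the observed difference is 0.1965 × 0.3 × 0.220 = 0.013, or 11% of the margin. At r = 0.2 it is 0.009 and at r = 0.5 it is 0.022. These shifts average to zero over randomizations, and the crude standard error already includes them.

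**The case against.** The strongest reply is that nothing here is wrong. A randomized 1:1 comparison of crude proportions is valid, its standard error allows for chance baseline differences, and the plan and its power calculation use the same test. All of that stands.

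Four more specific objections:

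- **The contrast with 13.5.3.1.2.** A reader might infer that the protocol contradicts itself by adjusting in one IOP analysis and not the other. It does not. The outcome there is a change from baseline, so including baseline is routine, and it does not show that the sponsor regards baseline IOP as prognostic for reaching 30 mmHg.
- **The unknown correlation.** Two features of the design push r down: the cap at 24 mmHg, and a preoperative measurement taken up to 60 days before surgery. This stands, and is why the lower end of the range deserves more weight.
- **Cost.** A reader might infer that adjustment is free. It needs no new data, but it replaces a simple Wald difference with a model, a matching standard error and a fallback, on about 19 expected events per arm. This also stands.
- **Subgroups.** Section 13.5.1 repeats the analysis separately for subjects with and without IOP-reducing intervention. Section 9.3.4 calls for treatment at 30 mmHg or above, so spikes should be nearly absent in the untreated group and a logistic model there would be sparse or separated. The model should not be carried into these subgroups.

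The chi-square superiority test in 13.5.3.1.1 is also unadjusted, but no gain has been calculated for it and none is claimed.

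**Conclusion.** The point holds as an optional improvement of low priority. Baseline IOP is collected, is already in the imputation model, and could be used in the co-primary estimate without changing the estimand or the margin. For an assumed r of 0.2 to 0.5, about 1% to 11% of the variance is removed and power rises from 95.17% to about 95.4% to 96.9%. The likely gain is under about one percentage point, and at r = 0 there is none.

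A reader might infer that the crude analysis is biased, leaves imbalance unaccounted for, or underpowers the trial. The documents support none of these: the test is valid and the stated power is correct for it.

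All power figures above assume the one-sided 0.05 level of 13.3.1. Section 13.5.1 also treats the upper limit of a two-sided 95% interval as equivalent to a one-sided 95% limit. If the two-sided limit were used, the one-sided level would be 0.025 and unadjusted power 91.1%. That is a separate and larger question, which baseline adjustment does not settle.

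**What to change.** If the sponsor wants the gain, amend 13.5.1, or the SAP to which section 13 defers further detail, before unmasking:

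1. Within each imputed dataset, fit a logistic model of spike on treatment and baseline IOP.
2. From it, estimate the standardized (marginal) difference in proportions with a delta-method or robust standard error. An odds ratio would not do, because the margin is a difference in proportions.
3. Combine over imputations by Rubin's rules and compare the upper limit with 0.117.
4. Keep the crude Wald difference as a sensitivity analysis, and as the fallback under a non-convergence rule written in advance so that the choice of estimator cannot depend on the result.
5. Keep the crude method for the subgroups with and without IOP-reducing intervention.

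The cost is a paragraph of text, a few lines of code and slightly more complex modelling with few events. No extra data or subjects are needed. Leaving 13.5.1 unadjusted is also defensible.
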